Power Analysis. Previous research¹⁰⁷ suggests that an intervention that is similar to BBTF could produce an improvement in father engagement ($d = .42$).¹⁰⁸ Assuming an effect size of $d = .42$, a one-tailed alpha of .05, and a sample size of 144 participants (72 per group), we obtained a power of .80 for this design. Assuming a 20% dropout rate, the total sample needs to be 180 participants, 90 per group.

Sample Recruitment. Three recruiters, ethnically matched to the participants and with ties to the community, were trained in minority outreach by the research team to establish relationships with fathers that supported recruitment. They were also trained to give presentations about the program to community groups. It was essential that the data collectors hired were comfortable in low-income communities, highly personable, and very patient (particularly when parents failed to show up for appointments). All program advertisements included a brief description of a self-improvement program for AA fathers, featured photographs of scenes of fathers meeting together, and provided a number to call and e-mail address for further information. We continued with the highly successful active (recruiters meet directly with potential participants) and passive (potential participants are prompted to contact the staff) recruitment strategies used in our extensive prior work in low-income Chicago communities.^{95,104,105} Recruiters met with key informants already identified from churches, barbershops, community centers, schools, day care centers, local business establishments, dry cleaners, and sports venues to obtain the anticipated broad reach. Key informants were given brochures/flyers to pass on the information to potential participants. In addition, notices were placed in church bulletins and community newspapers. Active strategies included giving presentations at community churches and other community gathering places.

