Data Analysis Data analysis is described with respect to the three specific aims and hypotheses that were tested. Missing data was imputed using SAS Proc MI, a multiple imputation computer program based on the work of Rubin.¹³¹ All continuous data was examined for statistical normality. Histograms were obtained for these variables, and skew and kurtosis were assessed in order to assess statistical normality. Where possible, we normalized these data using Tukey's ladder of transformation¹³² before conducting statistical analysis. SPSS for Windows (Version 11) and SAS (Version 9.1) was used for data management and statistical analysis. A two-tailed 0.05 significance level was used for all statistical tests except where noted below. All analyses were performed on an intent-to-treat basis. Outcome measures that could be successfully transformed to achieve normality were in all likelihood close enough to a normal distribution that the robust nature of the F-test made it possible to obtain reasonable p values in the study.

Descriptive statistics on the sample data for all research variables were obtained. In addition, one-way ANOVAs and chi-square analysis on the demographic and baseline research measures were performed between the intervention and control groups to determine that they

were comparable. The effects of participant attrition on the research variable were also assessed using one-way ANOVAs.

Hypothesis 1: Relative to the attention control condition, BBTF program fathers will report better father outcomes (psychological well-being, parenting competence, and father-mother relationship quality) and greater paternal involvement (material support, in-kind support, father-child interaction) at 12 weeks and 24 weeks.

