Data analysis were a repeated measures analysis of variance (RM-ANOVA) to address Hypothesis 1. The basic design for these analyses was a 2x3 design with three assessment time points (the within-subjects factor) crossed with the two treatment conditions (BBTF and the comparison group [the between-subjects factor]). The null hypothesis for all these analyses was that changes for all dependent measures (psychological well-being, parenting competence, father-mother relationship quality, material support, in-kind support, and father-child interaction) would remain constant for the two groups over time. The alternative hypothesis was that they would increase over time in the BBTF group relative to the control group. This was the interaction effect in the RM-ANOVA. An initial multivariate analysis was be conducted first to see if there was any overall effect. If the null hypothesis was rejected in the multivariate analysis, we examined the univariate analyses. We tested for violations of sphericity, and if they were in evidence, then a Greenhouse-Geisser correction was used to estimate probability values.

In order to determine when these changes occurred across the three assessment time points, a follow-up analysis was conducted with time reparameterized into a set of two orthogonal Helmert contrasts. The two contrasts were of the form (1, -1/2, -1/2; 0, 1, -1), where if the first contrast was significant, this indicated that the critical differences occurred between times 1 and 2; and if the second was significant, the changes took place between times 2 and 3. This informed us as to the transition point or points where the velocity changes were greatest between the treatment and comparison groups.

Hypothesis 2: Across both conditions, father outcomes and post-intervention ratings of father-mother relationship quality will mediate paternal involvement at 12 weeks and 24 weeks.

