This analysis used a regression approach to mediation analysis, as that described in MacKinnon, 2008.¹³³ This approach looked at the extent to which changes in paternal involvement over time were explained by changes in the father outcomes and the mother-father relationship in both the treatment and control groups. This effect was estimated using a series of three regression analyses. The dependent variable (a measure of paternal involvement) at Time 2 (12 weeks) was regressed on a dummy-coded treatment variable and the same paternal involvement measure at Time 1 (baseline). Then the mediators (father outcomes and mother-father relationship) were included in the regression models, and the change in R-squared was used to determine their impact. These analyses were repeated for Times 1 and 3 (24 weeks).

Hypothesis 3a: Relative to the attention control group, BBTF children will have improved child outcomes (behavioral, emotional, and social) at 12 weeks and 24 weeks.

The analysis of Hypothesis 3a was directly parallel those described for Hypothesis 1. The only difference was in the dependent measures, which were be child outcomes instead of paternal involvement outcomes.

Hypothesis 3b: Across both conditions, father outcomes, father-mother relationship and paternal involvement will mediate child outcomes at 12 weeks and 24 weeks.

This analysis used the same regression approach to mediation analysis described in Hypothesis 2, with the only differences being that the outcome variable was the child outcomes

rather than paternal involvement; paternal involvement acted as a mediator along with father outcomes and father-mother relationship.

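### Hypotheses 1 and 3a are tested by a 2-df group-by-time interaction with baseline as an outcome level: valid, but less efficient than a baseline-adjusted test of the 12- and 24-week values

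*Combined protocol and SAP*

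**What the plan says.** Under Data Analysis, Hypothesis 1: "The basic design for these analyses was a 2x3 design with three assessment time points", crossed with the two conditions. The three time points are baseline, 12 weeks and 24 weeks. The stated alternative is an increase over time in the intervention group relative to control, and "This was the interaction effect in the RM-ANOVA". A multivariate test comes first, and univariate results are examined only if it rejects. Greenhouse-Geisser is used if sphericity fails. Two Helmert contrasts follow, to locate the change in time. Hypothesis 3a takes the same analysis with child outcomes.

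Baseline measures are completed before randomisation (Sample Recruitment). For Hypothesis 2 the plan does condition on baseline: 12-week involvement is "regressed on a dummy-coded treatment variable and the same paternal involvement measure at Time 1 (baseline". No such comparison is planned for Hypothesis 1 or 3a.

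The Power Analysis takes d = .42, "a one-tailed alpha of .05" and 72 per group, and reports that "we obtained a power of .80 for this design". The Data Analysis section says: "A two-tailed 0.05 significance level was used for all statistical tests except where noted below". No exception for Hypothesis 1 follows.

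**The concern.** Baseline precedes assignment, so apart from chance it carries no group difference. The interaction nevertheless treats the baseline group difference as one of three quantities to be compared. In effect this tests unadjusted change, and the noise in the baseline means enters at full weight. Conditioning on baseline weights it by its correlation with follow-up, which is more efficient whenever that correlation is below 1.

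Two things are at stake. The main tests may be weaker than the same data allow. And a 2-df F statistic gives neither a direction nor a size of effect at 12 or 24 weeks, although Hypothesis 1 makes its prediction at those two visits.

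**Working it through.** **Inputs from the documents.** n = 72 per group, d = .42, allocation 1:1, three visits (Power Analysis; Overall Study Design); two-tailed .05 (Data Analysis).

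**Assumptions.** d is standardised on the follow-up SD. Variances are equal, with the same correlation r between every pair of visits; r is not given, so .3 to .8 is shown. Fathers are independent. The preliminary multivariate test is not modelled.

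**The plan's own figure.** Two-group noncentrality is d√(n/2) = .42 × √36 = 2.52. One-tailed power is Φ(2.52 − 1.645) = .809 (noncentral t with 142 df: .806), so the stated .80 reproduces as a simple one-tailed comparison of two means. Two-tailed, the noncentral t gives .706. Dropout: 144/.8 = 180. No r and no interaction enter that calculation.

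**Planned interaction.** df = (2−1)(3−1) = 2 and 2(144−2) = 284. Noncentrality = (n/2) × Σ(δ_t − mean δ)² / (1−r), where δ_t is the group difference at visit t. For a sustained effect (0, d, d) the sum is (2/3)d². Since (n/2)d² = 36 × .1764 = 6.3504, noncentrality is 4.2336/(1−r): 6.05, 8.47 and 14.11 at r = .3, .5 and .7.

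**Joint baseline-adjusted test, same numerator df.** Given baseline, each follow-up value has variance 1−r² and the two have covariance r−r². For a sustained effect, noncentrality = (n/2)d² × 2/[(1−r)(1+2r)] = 12.7008/[(1−r)(1+2r)]: 11.34, 12.70 and 17.64, with df 2 and 140. The ratio to the interaction is 3/(1+2r): 1.88, 1.50 and 1.25. For an effect at 12 weeks only, noncentrality = (n/2)d²(1+r)/[(1−r)(1+2r)], which is 9.53 at r = .5 against 8.47 for the interaction.

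| Effect pattern | r | Planned interaction (2 df) | Joint baseline-adjusted (2 df) |
|---|---|---|---|
| Sustained | .3 | .583 | .856 |
| | .5 | .739 | .895 |
| | .7 | .927 | .969 |
| | .8 | .989 | .995 |
| Halved by 24 weeks | .3 | .459 | .678 |
| | .5 | .605 | .748 |
| | .7 | .834 | .891 |
| | .8 | .953 | .969 |
| 12 weeks only | .3 | .583 | .670 |
| | .5 | .739 | .786 |
| | .7 | .927 | .939 |
| | .8 | .989 | .990 |

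**One-df comparators.** The plan's first Helmert contrast sets baseline against the mean of the two follow-ups. Its variance is 1.5(1−r), so under a sustained effect its noncentrality equals that of the interaction, now on 1 df. The baseline-adjusted follow-up mean has residual variance (1+r)/2 − r².

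| Effect pattern | r | First Helmert contrast | Adjusted follow-up mean |
|---|---|---|---|
| Sustained | .3 / .5 / .7 | .685 / .824 / .962 | .917 / .943 / .986 |
| 12 weeks only | .5 | .304 | .425 |

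Simulation (10,000 runs at each r, sustained effect) gave .58/.74/.93 for the interaction and .91/.94/.99 for the adjusted mean, in agreement. The joint test was computed by formula only.

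**The case against.** The strongest reply is that a repeated measures interaction is a valid test in a randomised trial and does address the alternative the plan states, a relative increase over time. That stands; no bias is alleged. Nor is having baseline on the outcome side a fault in itself: a longitudinal model that constrains the group means to be equal at baseline would recover the efficiency.

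A reader might set .917/.943/.986 for the adjusted follow-up mean against .583/.739/.927 and attribute the whole gap to baseline handling. That is too strong. The comparison also cuts 2 df to 1 and assumes equal effects at both visits. The plan's own 1-df Helmert contrast already reaches .685/.824/.962, and with an effect at 12 weeks only the adjusted mean does much worse than the planned test (.425 against .739 at r = .5). The fair comparison holds the df at 2. The Helmert contrast does not replace it: it is only a follow-up, uses unadjusted change and gives no separate estimate at each visit.

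A reader might also infer that the trial is underpowered. The documents do not support this, because they give no r: on these assumptions the interaction falls below .80 at r = .5 and exceeds it at r = .7. The Power Analysis also does not say which SD standardises d.

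Two further limits stand. The plan examines univariate results only after a multivariate test, so the figures are not the power of the full procedure. And both programmes are delivered to cohorts of 12 to 15 fathers (Procedures), so independence is an assumption for every figure here.

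**Conclusion.** The point holds as one of efficiency. At equal numerator df, conditioning on baseline beats the planned interaction under sustained, fading and 12-week-only effects at each r from .3 to .8. With a sustained effect the gain is about 27 percentage points at r = .3 (.856 − .583), 16 at r = .5 (.895 − .739), 4 at r = .7 (.969 − .927) and under 1 at r = .8. With an effect at 12 weeks only it is about 5 points at r = .5 (.786 − .739). The direction is secure. The size rests on an undocumented correlation, compound symmetry, d on the follow-up SD, independent fathers and no multivariate gate.

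The second part also holds: the planned F test does not directly estimate the differences at 12 and 24 weeks. A reader might go further and say that Hypothesis 1 calls for an adjusted mean difference. It does not; it predicts better outcomes at those visits, and adjusted differences are a direct way to report on that.

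**What to change.** For each Hypothesis 1 and 3a outcome, replace the RM-ANOVA interaction with a longitudinal model of the 12- and 24-week values. Fixed effects: baseline value, baseline-by-visit, condition, visit and condition-by-visit. Use an unstructured covariance, which makes the sphericity test and the Greenhouse-Geisser step unnecessary.

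- Prespecify the joint 2-df test of condition at 12 and 24 weeks as the primary test of each outcome.
- Report the adjusted difference at each visit with its confidence interval. These estimates can be pooled by Rubin's rules under the planned multiple imputation.
- Keep the multivariate gate, applied to the baseline-adjusted outcomes, or replace it with a stated multiplicity rule across the outcomes (six for Hypothesis 1). Dropping it without a replacement would loosen error control.
- Restate power for the chosen test with a stated r and sidedness.

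The cost is SAP wording and a few lines in the SAS the plan already names, with no new data. The condition is timing: the document describes conduct and analysis largely in the past tense, so adopt the change as primary only if outcome data have not been examined. Otherwise keep the planned test and report this model as supplementary.

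### Hypothesis 1 is sized for one direct comparison but tested through a multivariate first step and six unadjusted tests, which gives only weak familywise control and can cost power on the powered outcome

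*Combined protocol and SAP*

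**What the plan says.** The Power Analysis rests on one outcome. It cites earlier research that a similar intervention "could produce an improvement in father engagement", sets d = .42 with "a one-tailed alpha of .05" and 72 per group, and reports "we obtained a power of .80 for this design". It allows for 20% dropout. It makes no allowance for several outcomes or for a preliminary test.

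Under Hypothesis 1, the Data Analysis lists six dependent measures: psychological well-being, parenting competence, father-mother relationship quality, material support, in-kind support and father-child interaction. Each is tested by the group-by-time interaction over three assessments. A multivariate analysis comes first, and then: "If the null hypothesis was rejected in the multivariate analysis, we examined the univariate analyses". No multiplicity adjustment follows. The opening of the Data Analysis section sets two-tailed .05 for each test unless noted below, and no exception is noted later. No primary outcome is named.

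The child outcomes inherit the rule: "The analysis of Hypothesis 3a was directly parallel those described for Hypothesis 1".

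**The concern.** A multivariate first step protects the later univariate tests only while every null hypothesis is true. One real effect can open the way to the remaining outcomes, each then tested at the full .05. That is weak familywise control, and a trial that expects some real effects needs strong control.

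The first step also stands in front of the one outcome the trial was sized for. It can never raise the chance of claiming that outcome and may lower it, because an effect on one measure is diluted across all the contrasts in the multivariate test. At stake are a false claim on a father or paternal-involvement outcome, and a real effect of the planned size that is never formally tested.

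**Working it through.** **Stated power.** Inputs from the Power Analysis: d = .42, 72 per group, one-tailed .05. The standardised signal is .42 × √(72/2) = 2.52.
- One-tailed: Φ(2.52 − 1.645) = .81 (noncentral t: .806). The stated .80 reproduces, and 144/.8 = 180.
- Two-tailed, as the Data Analysis section requires: Φ(2.52 − 1.96) = .71 (noncentral t: .706). This fall has nothing to do with the multivariate step.

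**Assumptions not in the plan.** One Hotelling-type test covers six outcomes by two change contrasts (12 df). There are 72 per group. The visit correlation is .5 and the effect of .42 is present at both follow-ups. Outcomes share a common correlation ρ of 0, .3 or .5.

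**Chance that the first step rejects.** With unit SD, the two changes from baseline each have variance 2(1 − .5) = 1 and covariance .5. One affected outcome contributes .42² × 2/(1 + .5) = .2352. The noncentrality is λ = (72 × 72/144) × .2352 × c = 8.467c. For k of six outcomes affected, c = k/(1 − ρ) − ρk²/[(1 − ρ)(1 + 5ρ)]. Power comes from the noncentral F(12, 131). The last column comes from simulating the first step followed by the 2-df univariate tests.

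| Outcomes affected | λ at ρ = 0, .3, .5 | First step rejects | Powered outcome claimed |
|---|---|---|---|
| One | 8.5, 10.6, 14.5 | .39, .50, .66 | about .36 to .58 |
| Three | 25.4, 23.2, 29.0 | .92, .89, .96 | about .70 |
| Six | 50.8, 20.3, 14.5 | above .99, .84, .66 | .57 to .67 at ρ = .3 to .5; almost no loss at ρ = 0 |

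The comparator is the same 2-df test without the first step: noncentral F(2, 284) with λ = 8.47 gives .74, and simulation gives .73 to .75.

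**Sensitivity to visit correlation, one outcome affected.**
- At .7, the contribution is .42² × 2/(.6 + .3) = .392. The first step rejects in .65 to .91 of trials (ρ = 0 to .5), and the unscreened test has power .93 (λ = 36 × .392 = 14.1).
- At .3, the first step rejects in .28 to .35 (ρ = 0 to .3), and the unscreened test has power .58.

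**At least one false claim among the truly null outcomes (simulated).**
- All six null: about .03 to .05.
- One true effect of d = .42: about .15 to .16 among the other five.
- Three true effects of d = .42: about .13 to .15 among the other three.
- One true effect of d = .8: about .23 with uncorrelated outcomes, where the first step almost always rejects. The limit for five independent tests is 1 − .95⁵ = .226. Correlation between outcomes lowers it.
- All six real: zero, because no null outcome is left.

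**The case against.** The plan's own alternative is that all six measures improve. If so, no null outcome exists to be claimed falsely, and the one-outcome scenario with the largest power loss is not the one the investigators expect. With three outcomes affected, the first step costs almost nothing. Higher visit correlation shrinks the loss. This stands, and it is why the power figures must be given as a range. It does not remove the point. If all six improve and are moderately correlated, the claim rate still falls to .57 to .67, and if only some improve, error control fails even where power recovers.

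A reader might infer that the plan has no control of false claims at all. The documents do not support that, because the first step does hold error near .05 when nothing works. A reader might also set the lowest claim rate against the stated .80 and charge the whole gap to the first step. That is not supported either: the rate depends on correlations and on a number of affected outcomes that the plan does not give, and part of the gap is the separate change from one-tailed planning to two-tailed testing.

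Two further links are inferences. Father engagement is not, by that name, one of the six measures; it could mean father-child interaction or the wider paternal involvement domain. The plan also does not name the multivariate statistic or say that one test spans all six measures, although that is the natural reading.

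**Conclusion.** The concern holds in limited form. The sample size ignores both the multivariate first step and the number of outcomes, and the stated rule gives weak rather than strong familywise control. The excess false-claim risk arises only when real and null effects are mixed: two to three times the nominal .05 when the true effects are of the planned size, and more if one effect is large. The power loss on the powered outcome is possible but not established. Under the 12-df, visit-correlation .5 assumptions, it runs from almost nothing to about half of the unscreened power. The qualitative conclusion does not depend on those assumptions, but every power figure does.

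**What to change.** Name as the single primary outcome of Hypothesis 1 the measure that corresponds to the father engagement outcome behind d = .42. The sponsor must confirm which it is; father-child interaction is the likely match. Test it first at two-sided .05, without the multivariate step. If it is significant, test the other five with Holm's procedure; if not, report them as exploratory. Apply Holm to the three child outcomes of Hypothesis 3a (behavioral, emotional, social). Keep the multivariate test as descriptive.

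Restate the power for the test actually used: about .71 for a two-sided two-mean comparison at 72 per group. The reordering does not restore .80. That would need 2 × (1.96 + .842)²/.42² = 89 per group, or 178/.8 = 223 enrolled.

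The document is largely in the past tense. If outcome data have already been analysed, label the ordering post hoc and report Holm-adjusted p-values across all six outcomes.

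The change is to analysis wording and needs no new data. Its price is stricter thresholds for secondary outcomes. At the first Holm step of .05/5 = .01, power for d = .42 is about .47 (noncentral t with signal 2.52). Label: cheap improvement.

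### The first Helmert contrast compares baseline with the average of both follow-ups, so its significance does not place the effect between baseline and week 12

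*Combined protocol and SAP*

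**What the plan says.** Under Data Analysis, Hypothesis 1, the main test is the group-by-time interaction in a 2x3 repeated measures ANOVA. A multivariate test comes first: "If the null hypothesis was rejected in the multivariate analysis, we examined the univariate analyses". A follow-up analysis then asks when the changes took place. "The two contrasts were of the form (1, -1/2, -1/2; 0, 1, -1"), and the rule for the first is "if the first contrast was significant, this indicated that the critical differences occurred between times 1 and 2". A significant second contrast is read as change from time 2 to time 3. The section adds: "This informed us as to the transition point or points where the velocity changes were greatest between the treatment and comparison groups".

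The times are baseline, 12 weeks and 24 weeks. The alternative is stated as growth: "The alternative hypothesis was that they would increase over time in the BBTF group relative to the control group". Hypothesis 1 claims benefit at both follow-ups, for example "greater paternal involvement (material support, in-kind support, father-child interaction) at 12 weeks and 24 weeks". The same method carries over to child outcomes: "The analysis of Hypothesis 3a was directly parallel those described for Hypothesis 1". Overall Study Design places a booster session for both arms at week 18, between times 2 and 3.

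**The concern.** The first set of weights uses all three assessments, yet its significance is read as a statement about the first two only. That needs a group difference that is flat from week 12 to week 24, which is what the follow-up is meant to find out. The plan does not assume a plateau and does not make the reading depend on a null second contrast. It also includes no direct baseline-versus-week-12 contrast. The week-18 booster makes later change a real possibility, and the stated alternative allows growth in both intervals.

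What is at stake is the reported timing of effects for Hypotheses 1 and 3a: whether a difference arose during the 12-week program, after it, or arose and then faded.

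**Working it through.** **The plan's own figure.** Power Analysis gives power .80 for d = .42, 72 per group, one-tailed .05. The noncentrality is .42 x sqrt(72/2) = 2.52; on 142 df the noncentral t gives .806, so the figure reproduces. So does the inflated total, 144/(1 - .20) = 180. These planning values are reused below at the two-tailed .05 level that Data Analysis sets by default.

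**Algebra (no assumptions needed).** Let T1, T2, T3 be the between-group difference at each time; movement common to both arms cancels.

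- First contrast: T1 - (T2 + T3)/2 = (T1 - T2) + (T2 - T3)/2.
- Second contrast: T2 - T3, correctly read as times 2-3.

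Half of any change after week 12 therefore enters the first contrast. The two contrasts are orthogonal (1x0 - 1/2x1 + 1/2x1 = 0), but that does not turn the first into a times 1-2 comparison.

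**Standard errors.** Assumed: unit variance and equal within-person correlation rho = .3/.5/.7 (the documents give none).

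- First contrast: sqrt(2 x 1.5 x (1 - rho)/72) = .171/.144/.112.
- (1, -1, 0) and (0, 1, -1): sqrt(2 x 2 x (1 - rho)/72) = .197/.167/.129.

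**Example: effect only after week 12, rho = .5.** The first contrast has expected value 0 - (0 + .42)/2 = -.21, and .21/.144 = 1.46, so it is significant in 30% of trials. (1, -1, 0) has expected value 0 and is significant in 5%.

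**Patterns.** Single-contrast probabilities come from the noncentral t. Joint ones are products, because the Helmert pair is uncorrelated under these assumptions; simulation agrees. For full loss at rho = .5, times 2-3 alone is (1 - .304) x .706 = .49. Entries are for rho .3/.5/.7.

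| Group difference (T1, T2, T3) | First contrast significant | (1, -1, 0) significant | Rule names 1-2 only | 2-3 only | Both |
|---|---|---|---|---|---|
| Early, sustained (0, d, d) | .685/.824/.962 | .562/.706/.898 | 65/78/91% | 2/1/0% | 3/4/5% |
| Equal growth (0, d/2, d) | .449/.582/.799 | .185/.240/.365 | 37/44/51% | 10/10/7% | 8/14/29% |
| Half fade (0, d, d/2) | .449/.582/.799 | .562/.706/.898 | 37/44/51% | 10/10/7% | 8/14/29% |
| Late only (0, 0, d) | .231/.304/.462 | .05 | 10/9/5% | 43/49/48% | 13/21/41% |
| Full loss (0, d, 0) | .231/.304/.462 | .562/.706/.898 | 10/9/5% | 43/49/48% | 13/21/41% |

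Two features stand out. Under equal growth the rule names times 1-2 alone far more often than times 2-3 alone, although the two intervals contribute equally; with (1, -1, 0) and (0, 1, -1), each is named alone in 18%/22%/30%. Late-only and full-loss effects give identical rows, as do equal growth and half fade, because the printed rule uses significance and ignores sign.

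**Effect of the omnibus tests.** These figures count trials that pass the gate and also give the stated result.

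- *Univariate interaction F (2 and 284 df).* The false times 1-2 flag under a late effect is 21%/29%/46%. Full loss is placed in times 2-3 alone in about 36%/43%/46%. Equal growth is placed in times 1-2 alone in about 28%/37%/47%, and in times 2-3 alone in about 8%/8%/6%.
- *With a multivariate gate as well.* The plan does not give its form. Taken as Hotelling's T2 on six outcomes by two contrasts, with between-outcome correlation .2 or .5 and the effect in one or all six outcomes, the late-effect false flag is 12-19%/19-28%/39-46%. Full loss is placed in times 2-3 alone in 16-31%/22-41%/31-47%.

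**The case against.** The best defence is that Hypothesis 1 expects benefit at both 12 and 24 weeks. If the effect appears early and lasts, the printed reading is right and the first contrast is more powerful than the direct one. With three-quarters of the gain kept, the two are about equal (57%/72%/90% for the first contrast). With a half fade the gain is usually still placed in times 1-2, and under equal growth a times 1-2 flag is true. All of this stands. It limits plainly wrong dating to effects that come late or are lost.

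Second, the contrasts are read as a pair. Under a late-only effect, most false times 1-2 flags come with a correct times 2-3 flag; times 1-2 is the only interval named in 10%/9%/5%. That is fair, but a false claim of change by week 12 is still false when a true claim stands beside it.

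Third, other output would help. Data Analysis promises descriptive statistics, and signed estimates would expose a reversal, although the printed rule uses neither. Under Hypothesis 2, "The dependent variable (a measure of paternal involvement) at Time 2 (12 weeks) was regressed on a dummy-coded treatment variable" with baseline as covariate. Before mediators enter, this gives an adjusted 12-week difference, and it is repeated for 24 weeks; Hypothesis 3b does the same for child outcomes. No such model is described with psychological well-being, parenting competence or father-mother relationship quality as the outcome. Three regressions are announced and only two steps are clearly described, so that gap is less than certain.

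**Conclusion.** The concern holds. The stated reading of the first contrast does not follow from its weights, and this depends on no assumption about the data. The percentages are illustrative: they rest on d = .42, 72 per group, unit variance, equal within-person correlations of .3 to .7 and the chosen effect patterns. On that basis, a late effect is falsely dated to times 1-2 in 23% to 46% of trials before any gate. A fully lost gain is credited to times 2-3 alone in 43% to 49%. The gates reduce these rates without removing them.

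The damage is confined to timing statements for Hypotheses 1 and 3a. The rule should be corrected because it can produce wrong statements about when the program worked and the remedy is small.

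**What to change.** Describe the first contrast as baseline versus the average of the two follow-ups. Keep the second as times 2-3, and report both as signed estimates. Base any claim about times 1-2 on (1, -1, 0), or on baseline-adjusted treatment differences at 12 and at 24 weeks, given for every Hypothesis 1 and 3a outcome.

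No new data are needed: the change is one of wording, plus one contrast or model statement per outcome. Relabelling alone costs no power and keeps orthogonality, but the contrasts then support no times 1-2 claim. Adding (1, -1, 0) has three costs:

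- It is one more test per outcome, correlated -.5 with (0, 1, -1) under equal within-person correlations.
- It has less power for an early, sustained effect (.56/.71/.90 against .69/.82/.96).
- Under equal growth, the direct pair names no interval in 64%/54%/33% of trials, against 45%/32%/13% for the Helmert pair.
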